## 2.3 Treatment Assignment and Blinding

Study intervention is defined as the medical device (CoolSculpting Elite System and CoolSculpting Elite applicators) intended to be administered to a study participant according to the study protocol.

At screening, after the participant has signed the informed consent form (ICF), the participant will be assigned a screening number sequentially based on the order in which the participant is screened into the study at that particular site. The participant identification number (i.e., site ID concatenated with the participant screening number) will serve as the participant identification number on all study documents.

Participants will undergo a CoolSculpting Elite treatment in an outpatient clinical setting. A treatment is comprised of timed segments of cooling (treatment cycle) followed by 2 minutes of manual massage. Treatments will be administered according to the CoolSculpting Elite user manual that has been prepared for specific countries and provided to the study sites. The CoolSculpting Elite applicators available in this study depend on country clearances and can include Curve 240, Curve 150, Curve 120, Flat 165, Flat 125, Surface 150, and Curve 80.

Blinding is not applicable to this open-label, nonrandomized study. Blinding will only be employed for photograph review by an independent panel of physician reviewers with expertise in the areas of dermatology and/or plastic surgery.

## 2.4 Sample Size Determination

The sample size was planned to provide reasonable precision for the estimate of the primary effectiveness endpoint, overall satisfaction rate for the midsection of the various body areas treated with CoolSculpting.

Previous studies conducted on participants undergoing flank or abdominal fat reduction using the CoolSculpting device reported moderately high overall satisfaction rate.

A sample size of 96 participants would provide a two-sided 95% confidence interval (CI) with a width equal to 0.2 when the overall satisfaction rate is 63.9%. Exact (Clopper-Pearson) method from the commercial software PASS 2008 was used for the sample size calculation. Allowing for a 12% attrition rate during the study period, approximately 110 participants will be needed for recruitment into the study.

---

If local guidelines are in effect to prevent and mitigate the effects of a pandemic or natural disaster, it is possible that some participants may not be able to complete all site visits as indicated per protocol. To preserve the sample size calculation, additional participants may be enrolled if more than 12% of the participants fail to complete the Cryolipolysis Satisfaction Questionnaire (CSQ)-Midsection Item 1 at 12 weeks after the final treatment.

### **3.0 Endpoints**

#### **3.1 Primary Effectiveness Endpoint**

The primary effectiveness endpoint is the proportion of participants with “satisfied” or “very satisfied” on the Item 1 for the CSQ-Midsection, measured at 12-week follow-up of final treatment [Week 12 (Visit 8) for participants who receive 1 treatment session, or Week 20 (Visit 9) for participants who receive 2 treatment sessions, or 12 weeks +14 days post treatment session 2 for participants who had their treatment session 2 rescheduled because of the CoolSculpting® Elite treatment hold in the US on / after 24th August 2021].

#### **3.2 Secondary Effectiveness Endpoints**

The secondary effectiveness endpoints include:

- The proportion of participants who received treatment to abdomen and flank and one or more additional body areas for treatment with “satisfied” or “very satisfied” on CSQ-Overall Item 1 measured at 12-week follow-up of final treatment [Week 12 (Visit 8) for participants who receive only 1 treatment session to all treated body areas, or Week 20 (Visit 9) for participants who receive 2 treatment sessions to any or all treated body areas, or 12 weeks +14 days post treatment session 2 for participants who had their treatment session 2 rescheduled because of the CoolSculpting® Elite treatment hold in the US on / after 24th August 2021].
- The proportion of participants with “satisfied” or “very satisfied” on individual treated body area (upper arms, inner thighs, outer thighs, fat under chin) CSQ Item 1 measured at 12-week follow-up of final treatment [Week 12 (Visit 8) for participants who receive only 1 treatment session, or Week 20 (Visit 9) for participants who receive 2 treatment sessions, or 12 weeks +14 days post treatment session 2 for participants who had their treatment session 2 rescheduled because of the CoolSculpting® Elite treatment hold in the US on / after 24th August 2021] for the respective treated body areas.

---

If local guidelines are in effect to prevent and mitigate the effects of a pandemic or natural disaster, it is possible that some participants may not be able to complete all site visits as indicated per protocol. To preserve the sample size calculation, additional participants may be enrolled if more than 12% of the participants fail to complete the Cryolipolysis Satisfaction Questionnaire (CSQ)-Midsection Item 1 at 12 weeks after the final treatment.

### **3.0 Endpoints**

#### **3.1 Primary Effectiveness Endpoint**

The primary effectiveness endpoint is the proportion of participants with “satisfied” or “very satisfied” on the Item 1 for the CSQ-Midsection, measured at 12-week follow-up of final treatment [Week 12 (Visit 8) for participants who receive 1 treatment session, or Week 20 (Visit 9) for participants who receive 2 treatment sessions, or 12 weeks +14 days post treatment session 2 for participants who had their treatment session 2 rescheduled because of the CoolSculpting® Elite treatment hold in the US on / after 24th August 2021].

#### **3.2 Secondary Effectiveness Endpoints**

The secondary effectiveness endpoints include:

- The proportion of participants who received treatment to abdomen and flank and one or more additional body areas for treatment with “satisfied” or “very satisfied” on CSQ-Overall Item 1 measured at 12-week follow-up of final treatment [Week 12 (Visit 8) for participants who receive only 1 treatment session to all treated body areas, or Week 20 (Visit 9) for participants who receive 2 treatment sessions to any or all treated body areas, or 12 weeks +14 days post treatment session 2 for participants who had their treatment session 2 rescheduled because of the CoolSculpting® Elite treatment hold in the US on / after 24th August 2021].
- The proportion of participants with “satisfied” or “very satisfied” on individual treated body area (upper arms, inner thighs, outer thighs, fat under chin) CSQ Item 1 measured at 12-week follow-up of final treatment [Week 12 (Visit 8) for participants who receive only 1 treatment session, or Week 20 (Visit 9) for participants who receive 2 treatment sessions, or 12 weeks +14 days post treatment session 2 for participants who had their treatment session 2 rescheduled because of the CoolSculpting® Elite treatment hold in the US on / after 24th August 2021] for the respective treated body areas.

- Correct identification of baseline vs 12-week follow-up of final treatment [Week 12 (Visit 8) for participants who receive only 1 treatment session, or Week 20 (Visit 9) for participants who receive 2 treatment sessions, or 12 weeks +14 days post treatment session 2 for participants who had their treatment session 2 rescheduled because of the CoolSculpting® Elite treatment hold in the US on / after 24th August 2021] images of the treated body area(s) by at least two out of three blinded, independent reviewers for the following body areas:
  - Midsection
  - Upper arms
  - Inner thighs
  - Outer thighs
  - Submental area

Success will be defined as at least 70% correct identification of the pre-treatment images.

### 3.3 Exploratory Effectiveness Endpoints

The exploratory effectiveness endpoints include:

- [REDACTED]

### 3.4 Safety Endpoints

- Adverse events (AEs) and adverse device effects (ADEs); serious adverse events (SAEs), serious adverse device effects (SADEs)
- Unanticipated AEs or ADEs (including Unanticipated SAE/SADEs)
- Pain assessments (0 to 10 scale, 0=no pain and 10=the worst pain imaginable)
- Post-treatment clinical assessment – epidermal, dermal, or subcutaneous findings
- Post-treatment clinical assessment – alteration in sensation
- Medical device deficiencies

### 4.0 Analysis Populations

The following population sets will be used for the statistical analyses.

The Enrolled Population will consist of all participants who signed the informed consent.

The Safety Population will consist of all enrolled participants who received at least one cryolipolysis treatment cycle (started or completed).

The Evaluable Population 1 will consist of all participants who completed the cryolipolysis treatment plan to the midsection and completed the CSQ-Midsection Item 1 at 12 weeks after the final treatment measured at Visit 8 (Week 12) for participants who receive 1 treatment session, or at Visit 9 (Week 20) for participants who receive 2 treatment sessions, or at 12 weeks +14 days post treatment session 2 for participants who had their treatment session 2 rescheduled because of the CoolSculpting® Elite treatment hold in the US on / after 24th August 2021, and do not have any significant protocol deviation or violation.

The Evaluable Population 2 will consist of all participants who completed the cryolipolysis treatment plan for any other body areas (Upper Arms, Inner Thighs, Outer

Thighs and Submental Area) whether midsection treatment is completed or not, and do not have any significant protocol deviation or violation .

The Evaluable Population 3 will consist of all participants who completed the cryolipolysis treatment plan for any body areas (Midsection, Upper Arms, Inner Thighs, Outer Thighs and Submental Area) and do not have any significant protocol deviation or violation.

The Evaluable Population 4 will consist of all participants who completed the cryolipolysis treatment plan to the midsection and one or more additional body areas (Upper Arms, Inner Thighs, Outer Thighs and Submental Area) and do not have any significant protocol deviation or violation.

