### 9.3. Populations for Analyses

The following populations are defined for statistical analyses:

Population	Description
Enrolled	The enrolled population will consist of all participants who sign the informed consent.
Safety	The safety population will consist of all enrolled participants who receive a cryolipolysis treatment cycle (started or completed).
Evaluable	
 
The evaluable population for the primary endpoint will consist of all treated participants who completed the cryolipolysis treatment plan to the midsection and who completed the CSQ-Midsection Item 1 at 12 weeks after the final treatment measured at Visit 8 (Week 12) for participants who receive 1 treatment session and at Visit 9 (Week 20) for participants who receive 2 treatment sessions.
 
The evaluable population for other effectiveness endpoints will consist of all treated participants who completed the cryolipolysis treatment plan for any other body areas (whether midsection treatment completed or not).
 

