#### **7.5 Protocol Deviations and Violations**

A protocol deviation (PD) is any non-adherence to study procedures that does not result in additional risk to the participant. Protocol deviations will be reviewed and documented before database lock.

A protocol violation (PV) is any non-adherence to the protocol that may result in significant additional risk to the participant (eg, enrollment of a participant who does not meet the study criteria). A protocol violation can also be an event of non-adherence to GCPs that may impact participant safety (eg, failure to obtain proper consent before performing study procedures). Violations should be reported to the study sponsor and the IRB within 5 working days if they occur.

Significant PDs/PVs (equivalent to major PDs/PVs as collected in data) listed below will be identified before database lock. The number and percentage of participants with significant PDs/PVs will be summarized for the Safety Population. Significant PDs/PVs related to the following categories which impact the study conduct, data validity or integrity for the study outcomes will be included:

- Key inclusion criteria

- Key exclusion criteria
- Withdrawal criteria
- Treatment
- Concomitant medications
- Timeframe deviation

A listing will be provided for the Enrolled Population.

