## **8.0                   Handling of Potential Intercurrent Events for the Primary and Key Secondary Endpoints**

Not applicable.

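### The only planned primary satisfaction rate covers midsection plan and questionnaire completers without a significant deviation; no rate for everyone treated is prespecified

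*SAP*

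**What the plan says.** **Primary set.** SAP 4.0 states: "The Evaluable Population 1 will consist of all participants who completed the cryolipolysis treatment plan to the midsection and completed the CSQ-Midsection Item 1" at the visit 12 weeks after final treatment. After a clause that keeps participants rescheduled because of the US treatment hold, the definition ends "24th August 2021, and do not have any significant protocol deviation or violation".

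**Protocol counterpart.** Protocol 9.3 states: "The evaluable population for the primary endpoint will consist of all treated participants who completed the cryolipolysis treatment plan to the midsection" and who answered the same item at the same time. It has no deviation condition.

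**Deviations.** SAP 7.5 states: "Significant PDs/PVs (equivalent to major PDs/PVs as collected in data) listed below will be identified before database lock". The categories are key inclusion criteria, key exclusion criteria, withdrawal criteria, treatment, concomitant medications and timeframe.

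**Analysis.** SAP 9.3.2 gives the percentage and exact 95% CI in Evaluable Population 1. SAP 9.2 allows no imputation. SAP 8.0, headed "Handling of Potential Intercurrent Events for the Primary and Key Secondary Endpoints", is marked not applicable, and so is 9.3.3 on sensitivity and supplementary analyses.

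**Other evaluable sets.** Population 2: "The Evaluable Population 2 will consist of all participants who completed the cryolipolysis treatment plan for any other body areas". Population 3: "The Evaluable Population 3 will consist of all participants who completed the cryolipolysis treatment plan for any body areas". Population 4: "all participants who completed the cryolipolysis treatment plan to the midsection and one or more additional body areas". Each also excludes significant deviations, and none requires a questionnaire.

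**Safety Population.** It receives disposition counts (5.0), interruptions and discontinuations with reasons and a completed-plan summary (6.0), counts of significant deviations (7.5) and a CSQ-Midsection listing (9.3.2). It receives no satisfaction rate.

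**The concern.** The main product of this open-label, single-arm study is one satisfaction percentage with its interval. Two of the three conditions for entering the denominator, plan completion and questionnaire completion, arise only after treatment starts. The third is mixed: eligibility deviations are fixed before treatment, whereas treatment, concomitant-medication, withdrawal and timeframe deviations are not. Which deviations count as significant is settled only before database lock.

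Protocol 7.1 lets treatment be stopped for discomfort or refusal, so leaving the evaluable set could plausibly be related to satisfaction. Protocol 7.2 encourages people who withdraw to complete the same final evaluations, yet a participant who did not complete the midsection plan has no place in the primary rate, even with a response.

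The same set is used for endpoints that do not need the questionnaire. The midsection row of the Week 4 noticeable-improvement item and the 4-week midsection photo review (SAP 9.5.2), and the 12-week midsection photo review (9.4.2), all use Population 1. A valid Week 4 answer or photo pair is therefore dropped if the separate 12-week questionnaire is missing. At stake is how these percentages are read: they describe completers, and no prespecified figure shows how far that matters.

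**Working it through.** **1. The plan's own figures.** Inputs from SAP 2.4 are 96 evaluable participants, a rate of 63.9%, an exact two-sided 95% CI of width 0.2, and 12% attrition. With x = 0.639 × 96 = 61.34, the Clopper-Pearson limits are 0.5346 and 0.7346: width 0.2000, half-width 10.0 points. For attrition, 96 / 0.88 = 109.1, rounded up to 110. Both figures reproduce.

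**2. Effect of leaving people out.** Let N be treated, m left out, p the rate in the evaluable set and q the share satisfied among those left out.

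- All-treated rate = [p(N − m) + qm] / N
- Reported rate minus all-treated rate = (p − q) × m / N

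**3. Assumed inputs.** The documents do not give the number treated. The 110 is a recruitment figure, and SAP 4.0 counts as enrolled everyone who signs consent, so fewer may be treated. I assume N = 110. Then m = 110 − 96 = 14, or 12.7%. Taking 12% of 110 gives 13.2, so 13 is shown too. These reflect planned attrition; deviation exclusions could add to them, so 20 is included as a further assumption.

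**4. Results for m = 14 at p = 63.9%.**

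- None satisfied (q = 0): 61.34 / 110 = 55.8%; error 0.639 × 14 / 110 = +8.13 points
- Same as the rest (q = p): 63.9%; error 0
- All satisfied (q = 1): (61.34 + 14) / 110 = 68.5%; error −0.361 × 14 / 110 = −4.59 points

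**5. Sensitivity.** The error in points at the two extremes, at the planning rate and at the 89.6% that protocol 2.2 reports for the earlier study:

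| Left out of 110 | 63.9%, none satisfied | 63.9%, all satisfied | 89.6%, none satisfied | 89.6%, all satisfied |
|---|---|---|---|---|
| 13 | +7.55 | −4.27 | +10.59 | −1.23 |
| 14 | +8.13 | −4.59 | +11.40 | −1.32 |
| 20 | +11.62 | −6.56 | +16.29 | −1.89 |

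At 63.9% with 13 or 14 left out, every shift is inside the 10.0-point half-width at 96 evaluable. At 89.6% the exact interval at 96 runs from 81.7% to 94.9%, a lower arm of 89.6 − 81.7 = 7.9 points, and the none-satisfied extreme is larger than that. The comparison gives scale only, because the interval covers sampling error and not selection.

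**The case against.** The study is descriptive. Protocol 9.1 and SAP 2.1 test no hypothesis, and the primary endpoint has no threshold, so no decision turns on the rate. The plan-completion and questionnaire conditions are openly stated in protocol 9.3, the sample size is set for people who complete the primary assessment, and protocol section 9 leaves populations and missing data to the SAP. Losses may be small: the second session is optional, treatment stopped for discomfort may be resumed (protocol 8.2.1), participants rescheduled after the US hold stay in Population 1, and withdrawing participants are asked for final evaluations. The Safety Population outputs are substantial, and the listing would allow an observed rate among treated responders to be counted. Scoring every non-responder as not satisfied would treat losses from travel restrictions as dissatisfaction.

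Most of this stands. It limits the weight of the point and rules out the all-not-satisfied figure as an estimate. It does not supply a prespecified rate, and it does not explain the deviation condition that the SAP adds to the protocol's definition. Nor does the general statement in SAP 9.1 that effectiveness is analysed in Populations 1 to 4 fill the gap, since all four require plan completion and exclude significant deviations.

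The Week 4 point is partly met: the any-area and all-areas rows use Population 3, which has no questionnaire condition. The midsection row and both midsection photo reviews do not.

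**Conclusion.** The gap in the text is clear: there is one primary rate, in a selected set narrower than the protocol's, with no supplementary rate planned. Its size is not known. The figure of 8.1 too high to 4.6 too low rests on the assumption of 110 treated and 96 evaluable at 63.9%; it is an illustration, not a forecast. Confidence is high for the gap and low for the magnitude. The point ranks between minor and should-fix.

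Four stronger readings are tempting and not supported:

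- That the rate is biased upward. Nothing in the documents shows how those left out would have answered; the error could be zero or negative.
- That the whole selection happens after treatment. Key eligibility deviations concern facts fixed beforehand.
- That nothing is reported for all treated participants. The counts, reasons and listing are planned; only a rate is missing.
- That SAP 9.4.3, which plans no supplementary analysis of the key secondary endpoints, also covers Population 3. Those endpoints use Populations 1, 2 and 4. The visible effectiveness analyses use Population 3 only for the exploratory Week 4 item, and parts of the exploratory and subgroup text are redacted.

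**What to change.** Keep the primary analysis as it is. In SAP 9.3.3, replace the not-applicable entry with two items:

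1. The observed 12-week CSQ-Midsection Item 1 rate, with exact 95% CI, in all Safety Population participants who had midsection treatment and gave a response, regardless of plan completion or deviations.
2. A range table over all midsection-treated participants, with missing responses set from all not satisfied to all satisfied. The all-not-satisfied row is a bound, not the estimate. This table is needed because item 1 still depends on having responded.

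Analyse the midsection Week 4 item and the 4-week and 12-week midsection photo reviews in treated participants who have the relevant assessment, without requiring the CSQ.

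Describe the primary result as applying to participants who completed the midsection plan and the 12-week questionnaire without a significant deviation. Label the key secondary results in Populations 2 and 4 as applying to plan completers without a significant deviation.

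The cost is SAP wording and two or three extra tables from data already collected. A less favourable rate may appear beside the headline.

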## 9. Statistical Considerations

The SAP will be developed and finalized before database lock and will describe the participant populations to be included in the analyses and procedures for accounting for missing, unused, and spurious data. This section is a summary of the planned statistical analyses.

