### **9.3.2 Main Analysis of Primary Effectiveness Endpoint(s)**

The CSQ consists of 6 versions: CSQ-Midsection, CSQ-Overall, CSQ-Upper Arms, CSQ-Inner Thighs, CSQ-Outer Thighs, CSQ-Fat under chin. However, only CSQ-Midsection will be used for the primary analysis. In each version, the CSQ Item 1 is about rating the participant overall satisfaction with the results of the fat reduction procedure on the treated body area based on the following categories:

- Very satisfied
- Satisfied
- Neither satisfied nor dissatisfied
- Dissatisfied
- Very dissatisfied

The number and percentage of participants with “satisfied” or “very satisfied” on the Item 1 for the CSQ-Midsection at Week 12 (Visit 8) for participants who receive 1 treatment session, or at Week 20 (Visit 9) for participants who receive 2 treatment sessions, or at 12 weeks +14 days post treatment session 2 for participants who had their treatment session 2 rescheduled because of the CoolSculpting® Elite treatment hold in the US on / after 24th August 2021 will be summarized for the Evaluable Population 1 and the two-sided Fisher’s exact 95% CI on the percentage will be provided.

A listing will be provided for CSQ-Midsection for the Safety Population.

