### **9.3.3 Sensitivity and Supplementary Analyses of the Primary Effectiveness Endpoint(s)**

Not applicable.

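### The SAP's primary analysis set drops participants with significant protocol deviations, the protocol's does not, and no analysis in the protocol's set is planned

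*SAP*

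**What the plan says.** Protocol 9.3: "The evaluable population for the primary endpoint will consist of all treated participants who completed the cryolipolysis treatment plan to the midsection" and who answered CSQ-Midsection Item 1 at the visit 12 weeks after their last session. For the remaining endpoints: "The evaluable population for other effectiveness endpoints will consist of all treated participants who completed the cryolipolysis treatment plan for any other body areas". Neither definition mentions deviations or violations. Protocol 9.4.1 bases the effectiveness analyses on the evaluable population.

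SAP 4.0 keeps the protocol's conditions for Evaluable Population 1, adds the timing for participants whose second session was rescheduled after the US treatment hold, and then adds "and do not have any significant protocol deviation or violation". Evaluable Populations 2, 3 and 4 carry the same clause.

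SAP 9.1 confines all effectiveness analyses to these four sets. Under SAP 9.3.2 the number and percentage satisfied "will be summarized for the Evaluable Population 1 and the two-sided" exact 95% interval is to accompany them. SAP 9.3.3, on sensitivity and supplementary analyses of the primary endpoint, is marked not applicable. The Safety Population gets only a listing of CSQ-Midsection.

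SAP 7.5 explains the term used in the clause: "Significant PDs/PVs (equivalent to major PDs/PVs as collected in data) listed below will be identified before database lock". It names six categories (key inclusion criteria, key exclusion criteria, withdrawal criteria, treatment, concomitant medications, timeframe), with the qualifier "which impact the study conduct, data validity or integrity for the study outcomes will be included".

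**The concern.** The trial's main result is one proportion with its confidence interval, so who enters the denominator determines the result. Under the SAP, that proportion comes from a more selected group than the protocol announces, and no planned table shows whether the difference matters. A reader could recover the protocol-defined rate only by rebuilding it from the Safety Population listings.

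The added exclusion is also not clearly unrelated to outcome. Two of the six categories are eligibility breaches. The other four can arise after treatment starts and so may be connected with how a participant fared. The study is open-label, the questionnaires are completed before lock, and nothing says that deviations are classified without sight of the CSQ answers.

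**Working it through.** **1. Definitions side by side**

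| Condition | Protocol 9.3, primary set | SAP 4.0, Evaluable Population 1 |
|---|---|---|
| Midsection treatment plan completed | yes | yes |
| CSQ-Midsection Item 1 completed 12 weeks after final treatment | yes | yes, with rescheduled visits added |
| No significant deviation or violation | not required | required |

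The third row is the discrepancy. Every set in SAP 9.1 carries the extra condition and SAP 9.3.3 is empty, so no planned effectiveness analysis uses the left-hand column.

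**2. The plan's own figure**

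Inputs from Protocol 9.2 and SAP 2.4: n = 96, satisfaction rate 63.9%, two-sided 95% Clopper-Pearson interval, width 0.2, 12% attrition, 110 enrolled.

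Lower limit = Beta quantile at 0.025 with parameters (x, n − x + 1). Upper limit = Beta quantile at 0.975 with parameters (x + 1, n − x).

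- With x = 0.639 × 96 = 61.344, the limits are 0.5346 and 0.7346 and the width is 0.19996. The smallest n with width at most 0.2 is 96.
- 96 / 0.88 = 109.1, rounded up to 110.

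Both stated figures reproduce.

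**3. Possible shift in the estimate**

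The documents give no count of completers with significant deviations, so 5 and 10 are assumed. The whole-number start nearest the planning rate is 61/96 = 63.5% (exact 95% CI 53.1% to 73.1%).

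If k completers are removed and a fraction q of them were satisfied, the new rate is (61 − qk) / (96 − k).

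| Removed (k) | All removed satisfied (q = 1) | Half satisfied (q = 0.5) | None satisfied (q = 0) |
|---|---|---|---|
| 5 | 56/91 = 61.5% | 58.5/91 = 64.3% | 61/91 = 67.0% |
| 10 | 51/86 = 59.3% | 56/86 = 65.1% | 61/86 = 70.9% |

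Against 63.5%, the extremes are −2.0 and +3.5 points for k = 5, and −4.2 and +7.4 points for k = 10. The shift is zero when q equals 61/96.

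**4. Loss of precision**

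At 63.9% the exact interval width is 0.200 for n = 96, 0.206 for n = 91 and 0.212 for n = 86. This is minor. The possible movement of the point estimate matters more.

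**The case against.** The strongest reply is that the protocol delegates the matter. Protocol 9 says the SAP "will describe the participant populations to be included in the analyses", gives it the handling of spurious data, and calls its own section a summary. Excluding records whose deviations damage data validity arguably falls within that. But adding detail differs from removing people whom an explicit protocol definition includes, and the visible SAP text neither acknowledges nor justifies the change. Part of the SAP version history is redacted next to the entry on the evaluable populations, so the statement is limited to the visible text. That entry also does not say when the clause came in.

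Other points reduce the weight:

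- The protocol's own conditions already remove some participants with treatment, withdrawal or timing deviations, so the clause's added effect is narrower than the six categories suggest. It is not nil: eligibility and concomitant-medication breaches, for example, can occur in full completers.
- Significant deviations correspond to a major category recorded in the data and are identified before database lock. That is a real safeguard on timing, but it is not masking to outcome.
- The SAP tabulates the size of each set, the number of participants with significant deviations, and baseline characteristics for both the Safety Population and Evaluable Population 1. These show the scale of exclusion but not the satisfaction rate with the excluded participants included.
- No hypothesis is tested, and even the extreme bounds for 10 removals stay inside the starting interval of 53.1% to 73.1%. This limits severity. It does not make the two populations the same.

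**Conclusion.** The concern holds. The SAP's primary set is narrower than the protocol's, and the protocol-defined proportion is not among the planned analyses. With 5 or 10 completers excluded, the reported rate could differ from the protocol-defined rate by up to 3.5 or 7.4 points upward, or 2.0 or 4.2 points downward. Those limits assume a start at 61/96 and that those removed were all satisfied or all not satisfied. The exclusion counts are also assumptions, and realistic shifts may be much smaller or zero. Selection related to outcome is possible but not shown. The plan should be corrected because this is the trial's main estimate, but no test or success threshold for the primary endpoint turns on it.

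**What to change.** In SAP 4.0, remove the deviation clause from Evaluable Population 1 so that it matches Protocol 9.3, keeping the update for rescheduled second sessions, and use it for the primary analysis. In SAP 9.3.3, replace the not-applicable entry with the same proportion and exact interval in the deviation-free subset, as a named sensitivity analysis.

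Treat the other sets consistently. Evaluable Population 2 has a direct counterpart in Protocol 9.3 and should follow it. Populations 3 and 4 have no separate counterpart there, but should drop the clause too, so that all effectiveness results rest on the same principle.

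As a supporting step, state in SAP 7.5 what makes a deviation significant in each category, and have the classification made by staff without access to CSQ, CGPQ or photo-review results.

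The cost is SAP wording and some additional tables. No new data are needed.
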